## 7.4. Primary Efficacy Endpoint

### 7.4.1. Primary Analysis of the Primary Endpoint

The primary endpoint of this study is the change in eGFR at Week 12. The change from baseline eGFR for patients treated with bardoxolone methyl is compared with placebo at Week 12 using mixed models repeated measures (MMRM) analysis with the following fixed factors: KDIGO strata (HEAT\_STRAT), treatment group (TRT), time (i.e., VISIT; analysis visit number), and the interaction between treatment and time (TRT x VISIT).

The trial design separates discontinuation of study drug from discontinuation of study follow-up. Therefore, patients may discontinue early from study drug while continuing follow-up with study visits and assessments. The primary analysis of eGFR at Week 12 uses available eGFR values irrespective of whether a patient is receiving treatment. The MMRM analysis uses all eGFR values collected through Week 12 according to analysis visits 1,2,4,6,8, and 12 (Section 5.3.3). An unstructured covariance matrix is used.

In the event the MMRM model with an unstructured covariance structure does not converge, the following covariance structures are substituted, in the order listed. Each subsequent covariance structure is used only if each previous covariance structure is used and no previous model converged.

1. Heterogeneous Toeplitz covariance structure (assuming different variances at each time point and that measurements taken closer together in time are more highly correlated than those taken farther apart).

2. Toeplitz covariance structure (assuming measurements taken closer together in time are more highly correlated than those taken farther apart).
3. First order auto-regressive [AR(1)] covariance structure (assuming measurements taken closer together in time are more highly correlated than those taken farther apart, but the correlation is more constrained than the Toeplitz structure).
4. Compound symmetry covariance structure (assuming equal correlation for measurements from a patient, regardless of how far apart in time they were taken). A compound symmetry covariance structure was assumed in the sample size calculation.

If the MMRM model does not converge using any of the aforementioned covariance structures, variables from the model statement may be removed.

The difference between bardoxolone methyl and placebo in change from baseline of eGFR is estimated along with the 95% confidence interval at Week 12 for the primary analysis of the primary endpoint.

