## 12. STATISTICS

### 12.1. Sample Size

With 70 patients enrolled (35 in each group), the study will have approximately 80% power to detect a difference between the two treatment groups in change from baseline in eGFR of 5.9 mL/min/1.73 m^2 for the primary endpoint at Week 12. The power calculation, which was based on a two-sided two-sample t-test, assumes the following:

- Two-sided Type I error rate of 0.05;
- Standard deviation of change from baseline in eGFR of 8 mL/min/1.73 m^2;
- A change from baseline in eGFR of approximately 5.9 mL/min/1.73 m^2;
- 15% drop-out and missing data will not be imputed.

Analysis of the primary endpoint will be based on the intent-to-treat (ITT) population and analyzed using mixed-model repeated measures (MMRM) with an unstructured covariance structure. The analysis method is expected to have at least as much power as the two-sample t-test used for study planning. Appropriate sensitivity analyses of the primary analysis will be specified in the Statistical Analysis Plan (SAP). The secondary efficacy endpoint will be tested for sufficiently large subgroups, but the study is not powered to show efficacy in the secondary efficacy endpoint.

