### 12.3. Statistical Analyses

A SAP detailing the analyses will be developed prior to database lock. All statistical analyses and data summaries will be performed using SAS® (Version 9.1 or higher) or other validated software. The SAP will serve as the final arbiter of all statistical analyses. Data will be summarized overall using descriptive statistics. Continuous data will be summarized with number of patients (n), mean, median, minimum, maximum, relevant quartiles, standard deviation, coefficient of variation, and geometric mean (where applicable). Categorical data will be summarized using frequency counts and percentages.

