### **12.3.1. Primary Analysis of Efficacy**

The ITT population, which includes all enrolled patients, will be used as the population for assessment of the primary efficacy endpoint.

The primary endpoint is change in eGFR at Week 12. A mixed-model repeated measures (MMRM) model will be used to compare patients randomized to bardoxolone methyl to patients randomized to placebo. The model will include change from baseline in eGFR as the dependent variable, baseline eGFR and CKD stage as covariates, patient as a random effect, and the following fixed factors: treatment group, protocol-scheduled nominal time point, and the interaction between treatment and time. Other covariates may be specified in the SAP. Time ordering is a repeated measure within patients. It is assumed that errors for different patients are independent with an unstructured covariance structure. Missing data will not be imputed for the primary analysis since all data collected will be included in the MMRM analysis. Appropriate sensitivity analyses will be performed and defined in the SAP. The secondary efficacy endpoint will be tested for sufficiently large subgroups, but the study is not powered to show efficacy in the secondary efficacy endpoint. Exploratory efficacy will be summarized descriptively.

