## 1.2. Background

The original study protocol has undergone the following amendment.

Protocol Revision Chronology:		
Protocol	18-NOV-2020	Original
Protocol Version 2	17-FEB-2021	Amendment 1

This SAP was developed in accordance with ICH E9 guideline. All decisions regarding final analysis, as defined in this SAP document, will be made prior to unblinding of the study data as described in Section 5.1. Further information can be found in the protocol.

The SAP is based on:

- Protocol 402-C-2002, Version 2.0, dated 17-FEB-2021
- ICH guidelines E4 and E9 (Statistical Principles for Clinical Trials)

This SAP describes the study populations, how variables are derived, how missing data are handled, and details concerning the statistical methods to be used to analyze the safety and efficacy data from Study 402-C-2002. Should the SAP and the protocol be inconsistent with respect to the planned analyses, the language of the SAP is governing.

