### 3.4. Randomization

Qualified patients will be randomized 1:1 to bardoxolone methyl or placebo at Day 1 using RTSM. Randomization will be stratified using the KDIGO CKD progression risk heat map (stratum 1 = yellow or orange; stratum 2 = red or dark red) based on screening eGFR and UACR using RTSM (KDIGO 2012; Levin, 2014).

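### The governing SAP's primary MMRM omits baseline eGFR and CKD stage, which the protocol specifies as covariates, and gives no reason; some precision may be lost

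*SAP*

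**What the plan says.** Protocol 12.3.1 defines the primary model for change in eGFR at Week 12 as an MMRM with treatment, time and their interaction as fixed factors, and with "baseline eGFR and CKD stage as covariates, patient as a random effect". It then adds "Other covariates may be specified in the SAP", which provides for additions and does not mention removals.

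SAP 7.4.1 gives the fixed factors as the KDIGO stratum, "treatment group (TRT), time (i.e., VISIT; analysis visit number), and the interaction between treatment and time (TRT x VISIT"). Table 7 of the SAP, which lists the model terms, has no entry for baseline eGFR or CKD stage. The stratum is the two-level randomization factor of SAP 3.4 ("stratum 1 = yellow or orange; stratum 2 = red or dark red"), built from screening eGFR and UACR.

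Both documents settle which text prevails. Protocol 12.3 says "The SAP will serve as the final arbiter of all statistical analyses", and SAP 1.2 says "Should the SAP and the protocol be inconsistent with respect to the planned analyses, the language of the SAP is governing". SAP 1.2 also commits that "All decisions regarding final analysis, as defined in this SAP document, will be made prior to unblinding of the study data".

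The sample-size section of the protocol (12.1) uses an unadjusted two-sample t-test and assumes "15% drop-out and missing data will not be imputed".

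**The concern.** Two controlled documents describe different models for the only primary efficacy analysis. The shorter model is the binding one, and neither SAP 7.4.1 nor the SAP change summary (13.1) says why two covariates went. The secondary analysis (7.5.1) and the subgroup models (7.3) inherit the primary model.

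Two things are at stake.

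- **Precision.** If baseline eGFR predicts the change in eGFR, leaving it out gives a larger standard error at Week 12 than the data allow. The stratum adjusts for only part of it.
- **Missing data.** With 15% drop-out planned and no imputation, the MMRM relies on missing-at-random given stratum, treatment, visit and the observed changes. As the SAP is written, continuous baseline eGFR is not among the conditioning variables. Both Week 12 ANCOVA sensitivity analyses (7.4.1.1 and 7.4.1.2) list only stratum and treatment, so they do not test this choice.

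Those ANCOVA models, the off-treatment MMRM (8.1.1) and the off-treatment ANCOVAs (8.1.1.1, 8.1.1.2) also list no continuous covariate. The protocol does not specify any of these models, so nothing was dropped there. Outside the primary model, baseline eGFR enters the efficacy analyses only as a descriptive subgroup factor (7.3).

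**Working it through.** **Inputs from Protocol 12.1:** difference 5.9, SD of change 8, two-sided alpha 0.05, 35 per arm, 15% drop-out.

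**1. Reproduce the planned power.** Evaluable n per arm = 35 × 0.85 = 29.75. SE of the difference = 8 × √(2/29.75) = 2.074. Noncentrality = 5.9/2.074 = 2.844 on 2 × 29.75 − 2 = 57.5 df. Power by noncentral t = 79.9%, against the stated approximately 80%. The figure reproduces and involves no covariate.

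**2. Assumptions the documents do not supply.** These are illustrative.
- r, the within-arm correlation of baseline eGFR with change at Week 12: 0 to 0.4 in absolute value.
- eGFR uniform on 20 to 60; UACR log-normal with median 300 mg/g and log-SD 1.5; screening and baseline eGFR treated as equal.
- Heat-map colours in the UACR > 300 column are not legible in the text available, so two readings are shown with equal weight. In Reading A, stratum 2 is eGFR < 30, or 30–44 with UACR ≥ 30, or 45–59 with UACR > 300. In Reading B, the last group falls in stratum 1.
- Share of baseline eGFR variance explained by stratum (R²): 0.235 under A, 0.671 under B.

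**3. Formulas (single-visit approximation to the MMRM).**
- SAP model, stratum only: residual SD = 8√(1 − r²R²), df = 2n − 3 = 56.5.
- With baseline eGFR added: residual SD = 8√(1 − r²), df = 2n − 4 = 55.5, variance factor 1 + 1/(2n − 5) = 1 + 1/54.5 = 1.0183.

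Worked case, Reading A, |r| = 0.3. Without baseline: SD = 8√(1 − 0.09 × 0.235) = 7.915, SE = 2.052. With baseline: SD = 8√(1 − 0.09) = 7.632, SE = 7.632 × √(2/29.75 × 1.0183) = 1.997. The SE falls by 2.7%.

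**4. Results.** Power in %, without / with baseline eGFR.

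| abs(r) | A: power | A: change | A: SE change | B: power | B: change | B: SE change |
|---|---|---|---|---|---|---|
| 0 | 79.8 / 79.1 | −0.7 | +0.9% | 79.8 / 79.1 | −0.7 | +0.9% |
| 0.1 | 79.9 / 79.5 | −0.4 | +0.5% | 80.1 / 79.5 | −0.6 | +0.7% |
| 0.2 | 80.2 / 80.7 | +0.5 | −0.7% | 80.9 / 80.7 | −0.2 | +0.2% |
| 0.3 | 80.7 / 82.7 | +2.1 | −2.7% | 82.2 / 82.7 | +0.5 | −0.7% |
| 0.4 | 81.3 / 85.6 | +4.3 | −5.7% | 84.1 / 85.6 | +1.5 | −2.1% |

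Changes are taken from unrounded powers.

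**5. Break-even.** The SEs are equal when 1.0183(1 − r²) = 1 − r²R², so r² = 0.0183/(1.0183 − R²). This gives |r| = 0.153 under A and 0.230 under B. On the power scale the values are 0.156 and 0.234.

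**6. Sensitivity.** With UACR log-SD from 1.0 to 2.0, R² runs from 0.264 to 0.207 (A) and from 0.697 to 0.643 (B). Moving the UACR median to 100 or 1000 changes R² under A to about 0.37 or 0.09, but the SE break-even stays within 0.14 to 0.24 across both readings. A simulation (20,000 trials per r, 60 patients, allocation alternating within stratum) gave power changes of −0.9, −0.2, +0.4, +1.9 and +4.3 points (A) and −0.8, −0.8, −0.1, +0.7 and +1.4 points (B).

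**The case against.** The strongest counter-argument is that the SAP may be silent on covariates and not removing them. The protocol separates covariates from fixed factors. SAP 7.4.1 lists only fixed factors, repeats the protocol's three and adds the stratum. Calling a stratum-plus-treatment model an ANCOVA suggests that a covariate was meant. SAP 7 sends further model detail to a programming conventions document that is not available here. A drafting omission is therefore possible. It does not cure the SAP: the governing text, as written, does not contain the term, and if the programming document does, the SAP needs correcting.

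It is also fair to say that the SAP is entitled to depart from the protocol, that the stratum plausibly stands in for CKD stage and carries part of baseline eGFR, and that below the break-even the extra term costs a little precision. All of this stands, and it limits the size of the point.

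The calculation is a single-visit approximation. The real model uses six visits and partial data from drop-outs, and one baseline slope common to all visits need not equal the Week 12 slope while doses are being titrated. The figures are therefore indicative only.

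The missing-data point is not quantified. The plan keeps values collected after stopping drug, asks early discontinuers to keep attending, and includes a multiple-imputation analysis, all of which reduce the exposure. Finally, extending the change to the ANCOVA and off-treatment models is for consistency; the protocol does not require it.

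**Conclusion.** The concern holds. The governing primary model lacks two covariates that the protocol specifies, and no reason is given. This is not a power error or a type I error problem: the stated 80% does not depend on the covariates, and with complete data the test remains valid. The possible loss is precision. Under the assumptions above, restoring baseline eGFR changes power by −0.7 to +4.3 points under Reading A and by −0.7 to +1.5 points under Reading B for |r| from 0 to 0.4. Gains begin at |r| of about 0.15 (A) or 0.23 (B). Since the documents give no r, the direction of the effect cannot be settled from them. The discrepancy itself is certain; its effect on precision is modest and uncertain. It should be corrected, because it concerns the primary analysis and the correction is cheap.

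**What to change.** Before unblinding, amend the SAP as follows.

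1. Add continuous baseline eGFR as a covariate in 7.4.1 and Table 7, keeping the KDIGO stratum. Section 7.5.1 inherits the change.
2. For consistency, make the same addition in 7.4.1.1, 7.4.1.2, 8.1.1, 8.1.1.1 and 8.1.1.2.
3. State that the KDIGO stratum replaces the protocol's CKD-stage covariate.
4. Check that the programming conventions document specifies the same model.
5. If the omission is intended, give the reason in the SAP.

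The cost is an SAP amendment and one degree of freedom: about 0.7 power points if r = 0, and a small net loss for any |r| below the break-even. No new data are needed, because SAP 5.4.2 already derives baseline eGFR.

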### **7.5. Secondary Efficacy Endpoint**

#### **7.5.1. Primary Analysis of the Secondary Endpoint**

The secondary endpoint of this study is the change in eGFR at Week 12 by CKD etiologies (Diabetes, Hypertension, and Other). The change from baseline eGFR for patients treated with bardoxolone methyl is compared with placebo at Week 12 by CKD etiology using mixed models repeated measures (MMRM) analysis as defined in Section 7.4.1.

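### Three of the four covariance fallbacks for the eGFR MMRM assume one variance at every visit and no robust standard error is named, so a Week 12 interval from them can be too narrow if variance rises

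*SAP*

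**What the plan says.** SAP 7.4.1 fits change in eGFR at analysis visits 1, 2, 4, 6, 8 and 12. The terms are KDIGO stratum, treatment, visit and treatment by visit, with an unstructured covariance. The substitutes are heterogeneous Toeplitz, Toeplitz, AR(1) and "Compound symmetry covariance structure (assuming equal correlation for measurements from a patient, regardless of how far apart in time they were taken"), and each is used only when everything before it has failed to converge. Only the first substitute is described as letting variances differ by visit.

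Two sentences close the rule. One supports the final substitute: "A compound symmetry covariance structure was assumed in the sample size calculation". The other covers total failure: "If the MMRM model does not converge using any of the aforementioned covariance structures, variables from the model statement may be removed". It names no variable and no order of removal.

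The SAP states no standard-error or degrees-of-freedom method. SAP section 7 refers to a programming conventions document for further detail.

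The same ladder serves other analyses. SAP 7.5.1 compares the arms "by CKD etiology using mixed models repeated measures (MMRM) analysis as defined in Section 7.4.1", and SAP 8.1.1 uses it for the off-treatment visits.

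On sample size, Protocol 12.1 says: "The power calculation, which was based on a two-sided two-sample t-test, assumes the following" and then lists a two-sided alpha of 0.05, one SD of 8, a difference of 5.9 and 15% drop-out.

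**The concern.** A fallback rule is written for the day the preferred model fails, so its answers should be sound on that day. Here the later steps drop the feature that protects the Week 12 contrast, a variance of its own. Under Toeplitz, AR(1) or compound symmetry the Week 12 standard error is built from a variance averaged over all six visits. Early visits are close to baseline and come before the top of the titration (SAP 3.1: Week 4, or Week 6 when baseline UACR exceeds 300 mg/g). If their spread is smaller, it pulls the Week 12 standard error down. The Week 12 difference and its 95% interval are the trial's main result.

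Two side issues do not depend on any variance pattern. First, the removal clause would be applied after unblinding (SAP 4.1), although SAP 1.2 says decisions on the final analysis are made before it. If treatment by visit were removed, the model would no longer estimate a Week 12 effect. Second, the sentence supporting compound symmetry conflicts with the protocol's account of the sample size.

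**Working it through.** **1. The plan's own figure.** Inputs from Protocol 12.1: 35 per arm, difference 5.9, SD 8, two-sided alpha 0.05, 15% drop-out.
- Evaluable per arm: 35 x 0.85 = 29.75.
- SE = 8 x sqrt(2/29.75) = 2.074, and 5.9/2.074 = 2.844.
- Power = Phi(2.844 - 1.96) = 81.2%; the noncentral t gives 79.9%.

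This reproduces the stated 80% or so. A single-time-point t-test needs no within-patient covariance, so compound symmetry played no part in it.

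**2. Covariance parameters at six visits.** Unstructured 6 x 7/2 = 21; heterogeneous Toeplitz 6 + 5 = 11. Toeplitz, AR(1) and compound symmetry each have one variance.

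**3. Closed form.** With complete data and treatment by visit in the model, the Week 12 contrast is in effect the difference in Week 12 means. Under an equal-variance structure:

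model SE / true SE = sqrt(mean of the six visit variances) / (SD at Week 12)

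type I error = 2 x [1 - Phi(1.96 x ratio)]

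Example, SD rising in equal steps from 5 to 8: the variances are 25, 31.36, 38.44, 46.24, 54.76 and 64, with mean 259.8/6 = 43.3 and root 6.58. The ratio is 6.58/8 = 0.823. The model SE is 0.823 x 2.074 = 1.71 against a true 2.074, and type I error is 10.7%.

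All SD patterns below are assumptions.

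| SD by visit | Ratio | Type I error |
|---|---|---|
| Flat 8 | 1.000 | 5.0% |
| 7 to 8, both arms | 0.938 | 6.6% |
| 6 to 8, active arm only (placebo flat at 6) | 0.924 | 7.0% |
| 5 to 8, active arm only (placebo flat at 5) | 0.876 | 8.6% |
| Plateau 5, 6, 7, 8, 8, 8, both arms | 0.887 | 8.2% |
| 6 to 8, both arms, equal steps | 0.879 | 8.5% |
| 6, 6.2, 6.6, 7, 7.4, 8, both arms | 0.863 | 9.1% |
| 5 to 8, both arms, equal steps | 0.823 | 10.7% |
| 5, 5.3, 6, 6.6, 7.2, 8, both arms | 0.804 | 11.5% |
| 8 falling to 6, both arms | 1.172 | 2.2% |

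Steeper growth costs more: 4 to 8 gives 13.2% in both arms and 10.8% in the active arm only.

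**4. Simulation under the null.** 35 per arm, six visits, 15% monotone drop-out, REML, model-based SE. The compound symmetry and AR(1) fits on rising SDs used 900 runs per pattern, so a rate near 10% has a Monte Carlo error of about sqrt(0.1 x 0.9/900) = 1 point.
- Flat 8: about 4-5%.
- 6 to 8: about 8-10%.
- Plateau 5, 6, 7, 8, 8, 8: about 8-10%.
- 5 to 8: about 11-13% (true SE about 2.05, model SE about 1.61-1.68).
- 5 to 8 with Toeplitz (300 runs): about 10-11%.
- 5 to 8 with heterogeneous Toeplitz (120 runs, imprecise): about 5-6%, model SE 1.99 against 2.07.

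A separate run of 800 replicates on 5, 5.3, 6, 6.6, 7.2, 8 gave 12.5-13.4%, the top of the quoted range.

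**5. How often the ladder would be used by etiology.** The cap of about 40% in Protocol 7.1 is 0.4 x 70 = 28 patients. With two groups at the cap, the third has 70 - 56 = 14. Unstructured REML fits with 15% drop-out, 60 runs per size, converged as follows:

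| Patients in the fit | Converged |
|---|---|
| 28 | 100% |
| 23 | 100% |
| 18 | 100% |
| 14 | 97% |
| 10 | 53% |

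These used Fisher scoring on regular simulated data; SAS on real data may differ.

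**The case against.** The strongest reply is that the harm needs a chain of events. Unstructured and heterogeneous Toeplitz must both fail, and the second already allows unequal variances. Nothing suggests that both would fail with 70 patients and six visits. This stands, so a reader should not infer that the primary analysis itself carries a 9-13% error rate.

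A reader might also infer that the by-etiology fits, with 14-28 patients against 21 covariance parameters, make the fallback likely. The documents and the convergence check do not support that.
- Convergence was 97-100% in that range.
- SAP 7.5.1 does not say that etiologies are fitted separately, and SAP 7.3 lists etiology among subgroups handled in one model with interaction terms.
- Protocol 12.1 limits testing to sufficiently large subgroups, and SAP 5.1 makes these p-values nominal.

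Some risk remains: the 40% cap is approximate, SAP 7.5.1 sets no minimum group size, and convergence was only about half at 10 patients.

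It is tempting, too, to treat titration as proof that variance rises. It is not. Placebo patients receive no active drug, the scheduled escalation ends by Week 6, and under a strict null a drug without effect adds no variance. That is why the milder rows of the table matter.

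Model-based errors are inferred from the SAP's silence, and the programming document may specify otherwise. The pre-specified Week 12 ANCOVA (SAP 7.4.1.1, applied to etiology by 7.5.1.1) uses only Week 12 values and would help expose an understated MMRM error. It is a partial check, since the MMRM remains the primary result.

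On the compound-symmetry sentence, the text of SAP 3.3 is not readable in the public copy, so the comparison rests on Protocol 12.1.

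**Conclusion.** The point holds as a conditional weakness in a stated rule. If the ladder goes past heterogeneous Toeplitz, errors are model-based and variance rises toward Week 12, the Week 12 standard error is understated. For the patterns behind the quoted ranges the shortfall is about 6% (7 to 8) to 20% (5, 5.3, 6, 6.6, 7.2, 8). Type I error is then about 6.5-9% for mild, active-arm-only or plateau growth in closed form, with the simulated plateau reaching about 10%. It is about 9-13% for an SD of 5-6 rising to 8 in both arms. It is nominal for a constant SD and conservative for a falling one. Every figure depends on visit SDs that the documents do not give.

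Reaching these steps is unlikely for the primary analysis and possible, not likely, for a small etiology group. The effect in the off-treatment model was not sized.

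Two defects hold without these assumptions: the removal clause is open-ended, and the compound-symmetry sentence does not match the protocol's t-test. Neither changes a result unless the rule is invoked. Together they justify an inexpensive wording change.

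**What to change.** 1. In SAP 7.4.1, replace fallbacks 2-4 with structures that keep a variance for each visit, for example ARH(1) and then CSH. In a small simulation (120 runs) these gave standard errors of about 2.0 and stayed near nominal, against 1.57-1.75 for compound symmetry and AR(1). Alternatively, require a bias-corrected sandwich standard error whenever unstructured is not used; this option was not simulated. Either way, state the standard-error and degrees-of-freedom method in the SAP. SAP 7.5.1 and 8.1.1 inherit the change.
2. Replace the removal clause with a rule that treatment, visit and treatment by visit are always kept. That leaves the KDIGO stratum as the only removable term.
3. Delete the sentence linking compound symmetry to the sample size.
4. In SAP 7.5.1, specify one model with etiology by treatment by visit and a shared covariance. The extra terms in SAP 7.3 contain no visit interaction, so they would hold the etiology difference in effect constant over visits.

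The cost is SAP wording and standard mixed-model options. There are two small downsides: sandwich errors need a small-sample correction at this size, and the joint model assumes a common covariance across etiologies.
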